## **D6. Research Methods: Parents and Adolescents**

### **D 6.1: Procedures: Parents and adolescents.**

***Pre-assessment procedures.*** After parent and youth enrollment is complete in a given family, the research assistant will schedule a time for each to complete a baseline assessment session by telephone or in person (we expect that most will be by phone). Once scheduled, those parents who have elected to have a phone provided for adolescent by the study will be shipped an Android phone with a prepaid data plan, to arrive just before the scheduled baseline assessment session.

Also immediately after enrollment of parent and youth, the research assistant will create an account for each on the VillageWhere server. The purpose of this account is for each individual to have the ability to download the app to his/her smartphone (see below). The account name will be the individual's email address, and a password will be created for them.

***Parent and youth baseline assessment.*** The session will involve each participant completing a set of questionnaires related to the app's clinical targets (see measures section) and the family's demographics. During the session, the research assistant will introduce each measure, read items to the participant if necessary, and answer questions. Participants will respond to the questions using either an internet connection to the RedCap secure interface on the MUSC server, or on paper (participant will choose modality). If the session will be paper-based, research staff person will mail, email, or hand-carry measures to the family's home along

with a self-addressed stamped envelop for return before the scheduled session time. If by RedCap, the research assistant will email (or verbally provide) the link to the questionnaires to the participant during the session phone call. Parent and youth sessions will be conducted separately, and each participant's answers will remain confidential from the other's. We expect that most assessments will occur using RedCap.

After questionnaires are complete, the final part of the parent's baseline assessment session will be to schedule a post-usage assessment session for both parent and youth, give the parent the go-ahead to download the VillageWhere app, inform the parent how to do so, and provide brief instructions for app use (see "downloading the app" and "instructions for app usage" sections below).

Once both parent and youth baseline sessions are complete, the parent will receive a thank-you card by mail, thanking the family for completing the baseline assessment and informing them that \$35 compensation has been banked for them for the sessions (\$25 for parents, \$10 for youth; see below). The note will also remind parents that payment may take the form of a check made out to the parent or retention of the study-provided phone, and will be provided at the end of study procedures.

**Downloading the app.** Once both baseline sessions are complete, the parent and youth each will receive an email with a link to the VillageWhere server and his/her study-created password. The parent's activation email will be sent only to the parent; the youth's activation email will be sent to the youth and parent. Both activation emails will be sent immediately after both have completed the baseline assessment; participants will click on the link using their smartphone, enter their email address and password, and click to download the app. After this procedure is explained to the parent, the research assistant will offer to assist the parent or youth in downloading the app if desired, either immediately or in a subsequent phone call.

Research staff will monitor whether or not each participant has downloaded the app by looking on the server. If after one week of sending the initial activation email the participant has not downloaded the app, the research assistant will remind the participant to do so on day 7 (first reminder email) and every other day thereafter (days 9, 11, and 13) by email. If by day 14 the participant has still not downloaded the app, the research person will make two phone calls and two text message attempts to reach the participant during days 14-21. Participants who have not downloaded the app within 21 days of the baseline assessment session will be administratively withdrawn from the study.

The dyad's (parent and youth) app usage testing period will be considered to begin on the next calendar day after the second dyad member's app is downloaded (i.e., after whomever's app – parent's or youth's - is downloaded last).

**App data generation.** Any app usage by parent or youth participant will result in the generation of information about type, duration, and other details of use (e.g., time of day) by the app itself (see measures section); these data will be captured on the server and will be deidentified. These data are substantive indicators critical for meeting one of the study's goals, namely, to determine whether and how (what features, etc.) real-world consumers are likely to use the app.

**Family app usage periods and daily satisfaction ratings.** The study will use 2 different app usage testing period lengths, depending on the timing of participant enrollment:

- **Field-Based Beta Testing Group** - the first 4-6 parent-youth participants will test the app for 14 days. The purpose of this phase is to ensure that the app is "bug free" and features perform as expected before it is subjected to a full initial open trial. Only four parent-youth dyads will participate in this phase if early users experience no or only

minor, easily-fixed glitches with app functioning. Five or six parent-youth dyads will participate if we determine that fixes to the app were substantial enough that the product needs to be retested with several additional participants before the open trial. The field-based testing group can be viewed as a pilot phase for the open trial. Except for the shorter testing period and different usage instructions (see next section), the procedures for this group will be identical to those in the open trial group (e.g., compensation, baseline and post-testing batteries, therapist involvement, etc.).

- **Open Trial Group** – Twenty parent-youth dyads will test the app for 45 days. Data obtained from this group will be the main basis upon which substantive conclusions about the app's success (the aims of this study) will be drawn.

Once each day during the testing period, the app will prompt each participant to answer three questions regarding his or her satisfaction with the app on that day. Participants will respond to the questions directly on their phones (within the app). Answering the questions will take less than 5 minutes. Data generated by these daily prompts will be stored on the app server. If during field-based beta testing users complain about the frequency being too high and too intrusive, we will reduce the frequency of collection (e.g., to twice each week) based on initial user feedback.

Phone-based data collection (i.e., automatic app usage data and self-report daily satisfaction ratings) will cease the day after the last day of the testing period (i.e., day 15 or day 46, depending on group).

**Instructions for using the app.** Verbal instructions for how to use the app will be provided to parents as part of their baseline assessment session (see Parent and Youth Baseline Assessment Section, above). These instructions to parents will vary, depending on whether the parent is participating in the Field Test or the Open Trial. Those parents in the **Field Test** will be encouraged to use the app as much as possible over the next 2 weeks. These parents will be told that the purpose of this phase of app usage testing is to debug any remaining problems with the app, and so the research staff would greatly appreciate it if they made an effort to use the app every day and to explore all of its features. These parents will also be instructed to encourage the youth to use the app as much as possible during this period.

Parents participating in the **Open Trial** will be told that they should use the app in whatever ways they wish and using whatever degree of clinical support from the therapist all parties (parent, youth, and therapist) deem necessary or helpful.

**Post-usage assessment battery and exit interview.** When calling to schedule or to confirm a scheduled post-usage assessment session, research staff will inform parents that each participant's timely completion of the session (i.e., within 2 weeks of the testing period ending) will earn the participant an additional raffle ticket for the tablet computer lottery.

On or about day 15 (for Field Test participants) or 46 (for Open Trial participants), the parent and youth each will complete the post-usage assessment session, by phone or in person (most are expected to occur by phone). In these sessions, the same battery of questionnaires related to clinical targets will be administered (on paper or using RedCap), plus several questionnaires related to satisfaction with and acceptability of the app. The session will conclude with a 30-45 minute open-ended "exit" interview with a member of the research staff during which the participant will have an opportunity to share thoughts and opinions about the experience of using the app and offer any suggestions for improvement.

Before closing with the parent, the research assistant will ask the parent whether or not s/he would like to keep the youth's phone or return it, for those families in which the parent elected for the youth to use a study phone. If the parent elects to return the phone, a

preaddressed stamped mailing package will be mailed to the parent for shipping. If the parent elects to retain the phone, the parent will be reminded that the cost of the phone will be deducted from the parent-youth dyad's overall earnings for participation. As of this writing, basic Android-based smartphones ranged in price from \$40 - \$80. All participants electing to be given a phone will receive the same make and model phone, and the exact cost of the phone ultimately purchased for this project will be inserted in the appropriate spot on the VillageWhere Study Policy on Smartphone Use, Return, and Compensation form (currently blank; see Appendix 11). Parents who elect to return the study phone will be mailed a check for the total study compensation as soon as the phone is received and when both parent and youth post-usage assessment sessions have occurred. In families who did not use a study phone, a check will be mailed immediately upon completion of both participants' post-usage assessment session/exit interview.

**Post-study app usage.** Parents and youth will not be allowed to continue to use the server-supported features of the app after they end their participation in the study. Within two weeks of a parent-youth dyad completing all study procedures, the participating parent will receive an email stating that their VillageWhere app will expire in one week, and to please make arrangements accordingly. On the day of expiry, research staff will cancel the parent-youth dyad as users of the app on the server. On the day before the users are removed, the parent will receive one additional email alerting them to the cancellation. Although the features of the app that require server support (e.g., the GPS locator) will no longer function on parent and youth phones, other features (e.g., the youth's daily behavioral expectations depicted in the Game Plan feature) will still appear on participant phones and may be of some value to participants.

**D 6.2. Measures: Parents and adolescents.** Enrolled parents and adolescents will generate 4 types of data: a) self-report questionnaires administered before (pretest) and after (post-test) the app usage period; b) app usage data, generated by the app whenever the parent or adolescent uses it and automatically stored on the app's server; c) daily app satisfaction ratings, prompted by the app, completed directly on the phone, and stored on the app server; and d) an open-ended qualitatively-oriented exit interview.

**Self-report questionnaires.** Tables D6.2a and D6.2b outline the measures that will be administered to enrolled parents and youth, respectively, at pre- and/or post-usage assessment points. Full questionnaires are provided as Appendices 12 and 13 to this protocol. Measures pertaining to participant functioning and parenting behavior are all commonly used in studies with populations similar to those in the present study (adolescents presenting to treatment and their families), including intervention outcome studies, and are psychometrically sound (i.e., good reliability and predictive validity). Additional psychometric information about these measures is available upon request. With the exception of the history of arrest questions (collected for descriptive purposes), these measures are expected to show improvements over time as a result of VillageWhere app usage for those participants in the open trial.

A family demographics measure, administered only to parents, was created for this study in order to describe the sample. The System Usability Scale ([name] et al., 2009) is commonly used in product development studies and relates to the user's satisfaction with and opinion of the acceptability of VillageWhere. A brief technology use and comfort questionnaire was created for this study.

Note that any measure listed at only the pre- or post-time point will only be administered at that time point. All measures will be entered into the RedCap system for data collection.

**Table D6.2a. Parent Self-Report Measures**

CONSTRUCT	SCALE	# OF ITEMS PRE-TEST	# OF ITEMS POST-TEST	CITATION / OTHER INFORMATION
▪ Family demographics	Created for study	25	---	n/a
Youth Functioning				
▪ Rule-breaking behavior	Subscale of the Child Behavior Checklist (CBCL)	17	17	Achenbach & Rescorla (2007)
▪ Aggressive behavior	Subscale of the Child Behavior Checklist (CBCL)	18	18	Achenbach & Rescorla (2007)
▪ Anxious / depressed	Subscale of the Child Behavior Checklist (CBCL)	13	13	Achenbach & Rescorla (2007)
Parent Functioning and Behavior				
▪ Life stress	Perceived Stress Scale (PSS)	10	10	Cohen, Kamarack, & Mermelstein (1983)
▪ Sense of control and efficacy in parenting	Parent Locus of Control scale	20	20	Campis, Lyman, & Prentice-Dunn (1986)
▪ Supervision of youth behavior	Loeber Parenting Scale, Supervision subscale	8	8	Loeber, Farrington, Stouthamer-Loeber, & Van Kammen (1998)
▪ Discipline consistency	Loeber Parenting Scale, Discipline Consistency subscale	5	5	Loeber, Farrington, Stouthamer-Loeber, & Van Kammen (1998)
▪ Discipline effectiveness	Loeber Parenting Scale, Discipline Effectiveness subscale	3	3	Loeber, Farrington, Stouthamer-Loeber, & Van Kammen (1998)
▪ Rewards for youth good behavior	Loeber Parenting Scale, Positive Parenting subscale	9	9	Loeber, Farrington, Stouthamer-Loeber, & Van Kammen (1998)
App Acceptability and General Technology Use				
▪ App useability / acceptability	System Useability Scale	---	10	[name] et al. (2009)
▪ Use of and comfort with technology	Created for study	---	5	n/a

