**Table D6.2b. Youth Self-Report Measures**

CONSTRUCT	SCALE	# OF ITEMS PRE	# OF ITEMS POST	CITATION / OTHER INFORMATION
Youth Functioning				
▪ Rule-breaking behavior	Subscale of the Youth Self Report (YSR)	18	18	Achenbach & Rescorla (2007)
▪ Aggressive behavior	Subscale of the Youth Self Report (YSR)	18	18	Achenbach & Rescorla (2007)
▪ Anxious / depressed	Subscale of the Youth Self Report (YSR)	13	13	Achenbach & Rescorla (2007)
▪ History of arrest	Created for this study	3	---	n/a
▪ Alcohol and drug use	Center for Substance Abuse Prevention (CSAP)Scale	12	12	SAMHSA (2006)
Parent Behavior				
▪ Supervision of youth behavior	Loeber Parenting Scale, Supervision subscale	8	8	Loeber, Farrington, Stouthamer-Loeber, & Van Kammen (1998)
▪ Discipline consistency	Loeber Parenting Scale, Discipline Consistency subscale	5	5	Loeber, Farrington, Stouthamer-Loeber, & Van Kammen (1998)
▪ Discipline effectiveness	Loeber Parenting Scale, Discipline Effectiveness subscale	3	3	Loeber, Farrington, Stouthamer-Loeber, & Van Kammen (1998)
▪ Rewards for youth good behavior	Loeber Parenting Scale, Positive Parenting subscale	9	9	Loeber, Farrington, Stouthamer-Loeber, & Van Kammen (1998)
▪ Parental surveillance and knowledge	Parent Knowledge Scale	15	15	Steinberg, Elmen, & Mounts (1989)
App Acceptability and General Technology Use				
▪ App useability / acceptability	System Useability Scale	---	10	[name] et al. (2009)
▪ Use of and comfort with technology	Survey created for this study	---	5	n/a

**App usage data.** The App Usage Data Elements document within Appendix 14 outlines the data that will be generated by app usage itself for each participant (parent and youth). Examples of fields that will be generated are number of times each app component is opened, times of day opened, and participant responses to prompts. These data will be stored on the same server where the app operates and available for download after the dyad has completed their participation.

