**D7.3: Measures: Therapists.** Enrolled and participating herapists will provide data in two ways: 1) completing three questionnaires after all of their linked parent-youth dyads have completed study procedures; and 2) participating in an exit interview with study staff.

**Self-report questionnaires.** Table D7.3 outlines the measures that will be administered to enrolled therapists who have a linked parents-youth dyad. Full questionnaires are provided as Appendix 17 to this protocol. A therapist demographics measure asks about personal and professional characteristics and is collected for the purpose of describing the sample. Therapists will complete the brief technology use and comfort questionnaire created for all participants in this study, and will complete an additional survey regarding experiences with VillageWhere from the therapist perspective.

All therapist self-report measures will be collected one-time only, at the end of their participation in the study (i.e., when their last linked parent-youth dyad finishes its usage period and post-usage data collection sessions). Questionnaires will be entered into the RedCap system for data collection.

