**Table D7.3. Therapist Self-Report Measures**

CONSTRUCT	SCALE	NUMBER OF ITEMS
▪ Demographics	created for study	10
▪ Use of and comfort with technology	created for study	5
▪ Therapist experience with VillageWhere survey	created for study	6

*Note.* All therapist self-report items are administered only at the post-assessment time point.

**Exit interview.** After completing their self-report battery, therapists will participate in the same six-item open-ended exit interview used with parents and youth (see Appendix 16). The interview is expected to take 30-45 minutes to complete.

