## **D11. Data Analysis**

Data from demographics questionnaires and the Technology Use and Comfort Survey will be used to describe the sample itself. App usage and SUS data will be used to describe the success of the app itself. On the SUS, scores below a 3.5 on a five-point Likert scale (1 = poor; 2 = fair; 3 = good; 4 = very good; 5=excellent) will indicate a need for further app refinement in subsequent research. An aggregated mean score of 3.5 or higher will support app feasibility. App usage data will be aggregated and subjected to descriptive analyses to determine most preferred features and feature use sequences. Correlational analyses will link app usage data to participant satisfaction ratings and to measures of parent/youth behavior and functioning, to determine if certain app features were more highly preferred or more linked to changes in functioning than others.

Average scores on the SUS will also be compared between parents and adolescents. Between-group comparisons on the USAS will involve independent samples t-tests; effect size estimates also will be computed.

Pre- to post-usage change will be assessed on all parent and youth measures of functioning and behavior. Paired-samples T tests will be used and effect sizes obtained.

Qualitative data obtained from exit interviews will include annotations from investigators noting likes, dislikes, points of confusion, suggestions for improvement, misunderstandings, and potential unintended consequences. Qualitative data will be analyzed using a grounded theory approach (a data-reduction method for qualitative data used to generate and test hypotheses from the ground up).

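### The technology use and comfort survey is meant to describe the sample, but parents and youth answer it only after the app usage period, so it is not a baseline measure and is missing for non-downloaders and dropouts

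*Combined protocol and SAP*

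**What the plan says.** D11 states the purpose: "Data from demographics questionnaires and the Technology Use and Comfort Survey will be used to describe the sample itself".

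The schedule is in the measures tables. In Table D6.2a (parents) the row "Use of and comfort with technology" has a dash at pre-test and 5 items at post-test. In Table D6.2b (youth) the matching row, labelled "Survey created for this study", has the same pattern. D6.2 removes doubt about how to read the dash: "any measure listed at only the pre- or post-time point will only be administered at that time point".

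The timing of that session is in D6.1. On or about day 15 in the field test, or day 46 in the open trial, "the parent and youth each will complete the post-usage assessment session, by phone or in person".

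The other parent and youth descriptors are collected at pre-test. D6.2 says "A family demographics measure, administered only to parents, was created for this study in order to describe the sample", and Table D6.2a gives it 25 items at pre-test only. Youth history of arrest, which D6.2 says is collected for descriptive purposes, has 3 items at pre-test only.

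Therapists answer the same survey at the end of their participation. The note to Table D7.3 reads "All therapist self-report items are administered only at the post-assessment time point", and D7.3 says the table "outlines the measures that will be administered to enrolled therapists who have a linked parents-youth dyad".

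**The concern.** A measure that describes who entered a study is normally taken before the intervention and from everyone enrolled. This one is taken after it, from those who reach the last session. Two things follow.

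- **Exposure.** By the post-usage session a dyad has had the app for 14 days (field test) or 45 days (open trial), and some youth have been using a smartphone supplied by the study. Self-rated technology use and comfort could have changed by then. The answers are not baseline characteristics.
- **Coverage.** D6.1 withdraws participants who have not downloaded the app within 21 days of baseline. D9 foresees families who complete baseline but not the post-usage session. No catch-up assessment for either group is described, so neither supplies survey answers.

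At stake is the description of the sample and one feasibility question. Aim 3 sets out to identify further barriers to use, and comfort with technology is a natural candidate. As scheduled, the study cannot set the comfort of non-downloaders beside that of downloaders, or the comfort of dropouts beside that of completers.

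**Working it through.** **1. Purpose against timing**

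| Descriptor | Respondent | Pre-test items | Post-test items |
|---|---|---|---|
| Family demographics | Parent | 25 | none |
| History of arrest | Youth | 3 | none |
| Technology use and comfort | Parent | none | 5 |
| Technology use and comfort | Youth | none | 5 |

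The technology survey is the only parent or youth descriptor placed after the usage period. The plan gives no reason for the difference.

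**2. Enrolment figures**

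D4 plans 30 triads so that at least 24 complete. No dropout rate is stated. The figures imply (30 − 24)/30 = 20%, and 24/(1 − 0.20) = 30. This shows only that they are consistent with each other.

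**3. Parents and youth without survey answers (share of those enrolled)**

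- 30 enrolled, 24 complete: 6/30 = 20%.
- 30 enrolled, 26 complete (6 field test + 20 open trial, the upper allocation in D4): 4/30 = 13%.
- 26 enrolled, 24 complete: 2/26 = 8%.
- 24 enrolled, 24 complete: 0%.

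The 13% to 20% range therefore depends on enrolment reaching 30, which E1 gives as the maximum. In every case, all who do answer have already been exposed to the app.

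**4. Possible effect on the description (illustration; inputs assumed)**

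- Let 20% be missing and let a share p of respondents call themselves comfortable. The share among all enrolled then lies between 0.8p and 0.8p + 0.2. For p = 70% that is 56% to 76%; for p = 50%, 40% to 60%; for p = 90%, 72% to 92%.
- For a mean score, shift = missing share × gap between completers and dropouts. A gap of 0.5 SD gives 0.20 × 0.5 = 0.10 SD. Gaps of 0.25 and 1.0 SD give 0.05 and 0.20 SD.

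The documents give no figure for p or for the gap, so these results show possible size, not expected bias.

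**5. Would baseline collection reach the missing people?**

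D6.1 sends activation emails only after both members of the dyad have completed baseline. Every non-downloader will therefore have attended a baseline session and could have answered there. The same holds for those who leave during the usage period.

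**6. Burden of moving the items (sums of the table rows)**

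- Parent pre-test: 25 + 17 + 18 + 13 + 10 + 20 + 8 + 5 + 3 + 9 = 128, becoming 133.
- Youth pre-test: 18 + 18 + 13 + 3 + 12 + 8 + 5 + 3 + 9 + 15 = 104, becoming 109.
- Each post-test battery falls by 5.

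**7. Therapists**

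D4 and E1 allow up to 40 enrolled therapists. With 12 linked (D4's example) or 24 linked (one per dyad), (40 − 12)/40 = 70% or (40 − 24)/40 = 40% would not be surveyed. D7.2 says therapists have no pre-usage session, so there is no existing session to which their items could move.

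**The case against.** The schedule is not in dispute. The case on the other side is that the consequences are easily overstated, and much of it stands. A reader might infer four stronger things that the documents do not support.

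- **That the sample will look more comfortable with technology than the families approached.** Families who are approached but not enrolled never answer the survey at any time point, so its timing cannot create or close that gap. The eligibility rules (an Android smartphone with a data plan, and an email account) are a separate filter. The comparison has to be enrolled participants against those who reach the post-usage session, and the direction of any difference is an inference.
- **That low comfort is a likely cause of non-download or dropout.** D4's dropout examples are incarceration and phone service lost through unpaid bills; the latter concerns access or money rather than comfort. D6.1 also offers help with downloading, four reminder emails, and two calls and two texts. A link is plausible but undocumented.
- **That the lost dyads have no data.** Anyone who attends baseline supplies the pre-test battery, and download status is visible on the server. Only this survey and the other post-test measures are missing.
- **That 20% is the plan's dropout rate.** It requires 30 enrolled and exactly 24 completing. E1 also ties extra enrolment to further debugging in the field test, not only to dropout.

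Three further objections have some weight. First, contamination by exposure is not shown: the table heading refers to general technology use, and the items are in appendices not available here. Second, D11 does not define the sample. If it means those who supply System Usability Scale scores, also collected only at post-test, the coverage point weakens but the exposure point remains. Third, a baseline score would not support a test of dropout. With 24 completers against 6 dropouts, a two-sample t-test at two-sided 0.05 (assumed) has 80% power only for a difference of about 1.3 SD, and about 18% power for 0.5 SD. The gain is descriptive.

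None of this explains why one descriptor is collected after use when the others are collected before it.

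**Conclusion.** The point holds, and it is minor. Following the plan gives a sample descriptor measured after 14 or 45 days with the app, and missing for enrolled parents and youth who do not download it or do not complete the post-usage session. If 30 enrol, 4 to 6 of 30 (13% to 20%) are missing, with 26 or 24 completers; with lower enrolment the share is smaller.

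The coverage part assumes that the sample in D11 means those enrolled. It also rests on post-only timing, withdrawal of non-downloaders and the lack of any dropout assessment, since the plan nowhere says in so many words that only completers are surveyed. A light user who attends the last session is still counted. The exposure part needs no assumption about the order of events, but whether exposure shifts the answers is unknown.

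The description may therefore not represent everyone enrolled, and comfort cannot be described by download or completion status. No hypothesis test uses the survey, and no main conclusion depends on it.

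**What to change.** - In Tables D6.2a and D6.2b, move the 5 items from the post-test column to the pre-test column. Have them answered before the download instructions are given.
- In D11, say that the survey describes all enrolled parents and youth. Report it overall and by completion status, with non-downloaders shown separately, and give the number with no baseline session. Present the split as description only, because there will be too few non-completers for a test.
- Leave the therapist survey at post-assessment and label it as describing linked therapists only. State in the report that it was taken at a different time from the parent and youth versions.
- Check the items first. If any refer to experience with VillageWhere itself, keep those at post-test.

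The cost is 5 more items at baseline (128 to 133 for parents, 104 to 109 for youth) and 5 fewer at post-test. No new session or instrument is needed; the tables, D11 and the REDCap forms need a small edit.
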